#### **5.8.6.2    Body weight**

Body weight is collected at Visit 1 (Screening) and at Visit 6 (EOT). The following endpoint is defined:

- Change in body weight from baseline to EOT.

## 5.8.7 Electrocardiogram

### 5.8.7.1 12-lead ECG variables and findings

#### - 12-lead ECG variables

The 12-lead ECG measurements and qualitative ECG findings (e.g. rhythm, ectopy, conduction and morphology) are provided by the ECG central reader, along with the overall interpretation of the ECG (Normal/ Abnormal).

The following endpoints are defined:

- Absolute values and change from baseline to each post-baseline assessment up to EOS (i.e., each post-dose time point on Day 1 and each post-dose analysis visit up to EOS) for each parameter;
- Occurrence of treatment-emergent 12-lead ECG notable abnormalities;
- Occurrence of treatment-emergent 12-lead ECG qualitative abnormalities (medical review findings).

For the following ECG parameters, the occurrence of treatment emergent notable abnormalities is assessed according to the criteria defined in the table below.

**Table 7 Notable abnormalities in ECG parameters**

| Analysis Parameter  | Analysis Variable(s)                   | Analysis Criterion   |
|---|--|--|
| QTcB-Bazett's Correction Formula (ms) and QTcF-Fridericia's Correction Formula (ms) | Analysis value                         | - Value > 450 (male), Value > 470 (female)
- Value > 480
- Value > 500
- Value > 500 (male), Value > 520 (female) |
|   | Change from baseline                   | - Increase from baseline > 30
- Increase from baseline > 60   |
|   | Analysis value
Change from baseline | - Value > 450 and increase from baseline > 30
- Value > 450 and increase from baseline > 60                             |
| Heart rate (bpm)  | Analysis value                         | - Value < 40   |
| PR Duration (ms)  | Analysis value                         | - Value > 200  |
|   | Change from baseline                   | - Increase from baseline > 20  |
|   | Analysis value
Change from baseline | - Value > 200 and increase from baseline > 20  |

Notable abnormalities are derived for each post-baseline analysis visit. In addition, the occurrence of at least one abnormality on Day 1 (from 1 hour post-dose to discharge), after Day 1 (from discharge on Day 1 through EOT) and at any post-baseline analysis visit (from 1 hour post-dose through EOS) is also derived for each parameter for each subject.

- 12-lead ECG findings

For each ECG, the cardiologist provides his overall interpretation (Normal/ Abnormal) and describes the potential findings by category. All findings reported post first dose are considered as treatment-emergent.

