#### **11.4.3 Analysis of the safety variable(s)**

The Safety Analysis Set will be used to perform all safety analyses.

If not otherwise stated, only treatment-emergent safety data (observations with onset or assessment dates at/after first intake of study drug up to 6 weeks after study drug discontinuation) will be considered in tables and figures. All safety data will be included in listings, with flags for safety data not considered to be treatment-emergent.

Specific safety events (AEs, laboratory tests, ECG findings, etc.) will be considered. In general, they consist of one or more well-defined safety events that are similar in nature and for which there is a specific clinical interest in connection with ACT-334441.

For specific AESIs, the number and percentage of subjects with at least one event will be reported. Point estimates and 95% CIs for safety-event incidences and the relative risk ratio relative to placebo will be provided without adjustment for multiplicity.

Exploratory analysis of time to first onset of safety events of interest may be displayed by Kaplan-Meier estimates. Subjects not experiencing the safety event will be censored at the minimum of the EOS date and 6 weeks after last dose of study drug. Where applicable, study treatment doses will be compared with placebo by hazard ratios and corresponding 95% CIs from Cox's regression model.

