### **11.4.3.2 Cardiac safety**

#### *11.4.3.2.1 12-lead ECG assessments*

Descriptive summary statistics by visit and study treatment will be provided for observed treatment-emergent values and absolute changes from pre-dose in numeric 12-lead ECG values (HR, PR, QRS, QT, QTcB, QTcF). Data will be summarized from pre-dose to each post-dose assessments on Day 1 and also at the re-initiation of study drug.

Notable abnormalities for selected 12-lead ECG parameters (HR, PR, QT, QTcF) will be summarized for all data on Day 1, Week 12 and also at the re-initiation of study drug.

In addition treatment-emergent morphological ECG abnormalities will be summarized descriptively (using data from the ECG provider).

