#### *11.4.3.2.3 24-hour Holter ECG*

Treatment-emergent abnormalities as assessed by 24-hour Holter ECG monitoring will be summarized by dose group and presented similarly to AEs. Hourly mean HRs will be summarized descriptively.

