## Appendix 7 Notable abnormalities for ECG, BP and laboratory variables

### Notable abnormalities for ECG and BP

Notable abnormalities for ECG and BP that are related to the potential effects of ACT-334441 will address the following variables:

- Morphological ECG findings (defined as any abnormal finding not present prior to start of treatment)
- HR outliers (bpm), based on ECG
- PR interval (ms)
- QT/QTc interval (ms), based on Bazett's or Fridericia's formula
- BP (mmHg)

The definition of the abnormal values to be reported will be described in the SAP.

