**5.8.7.2 24 hour Holter-ECG**

Holter-ECG monitoring is performed for 24 hours at Visit 1 (Screening) and at Visit 2 (Randomization/ Day 1). The 24 hour Holter-ECG parameter collected is the hourly mean heart rate (bpm).

The hourly records are time-matched between these two visits and the corresponding change for each matched time point is computed.

The following endpoints are defined:

- Occurrence of treatment-emergent Holter-ECG-Holter abnormalities on Day 1;
- Absolute time-matched hourly mean heart rate (bpm) change from Visit 1 (Screening) to Visit 2 (Randomization/ Day 1) at each hourly timepoint up to 24 hours post-dose for;

- Holter-ECG- variables

The following analysis parameter is defined:

- ECG Mean Heart rate (beats/min) .

For this analysis parameter, the following analysis variables are defined (see Section 11 for further details):

- Baseline value at each hourly time point (i.e. hourly measurements at Visit 1)
- Analysis value at each post-baseline assessment (i.e., hourly measurements at Visit 2)
- Absolute time-matched change from Visit 1 (Screening) to Visit 2 (Randomization/ Day 1) at each hourly time point.

- Holter-ECG qualitative findings

For each Holter-ECG, the cardiologist provides his overall interpretation (Normal/ Abnormal) and describes the potential findings in the comment section. Each finding reported for the Holter-ECG performed on Day 1 are considered treatment-emergent.

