### **10.9.3 Electrocardiography (ECG)**

#### ***10.9.3.1 12-lead ECG variables and findings***

The following displays of ECGs are provided:

- Quantitative descriptive statistics for absolute values of ECG parameters by treatment group and analysis visit and time point.
- Quantitative descriptive statistics for the absolute change from baseline to 1h, 2h, 3h, 4h, 5h and 6 h post-dose on Day 1 and each post-baseline analysis visit by treatment group and parameter.
- Boxplots of absolute values at baseline and all post-baseline analysis visits and time points: one figure per parameter and per treatment group. Notable abnormality thresholds are displayed on the plots as an overlay.
- Notable ECG abnormalities for QTcB, QTcF, HR, PR and QRS are summarized by treatment group by presenting the number and percentage of subjects with any abnormality at each post-baseline analysis visit and time point, at any time on Day 1 (from 1 hour post-dose to discharge), at any time after Day 1 (from discharge on Day 1 up to EOT), and at any time post-baseline (from 1 hour post-dose to EOS), 95% Clopper-Pearson confidence intervals are presented for the proportions.
- The number and percentage of subjects with any treatment-emergent ECG qualitative abnormalities at any time (ECG findings) by category and reported term are summarized by treatment group.

The denominator for percentages is the number of subjects with at least one post-baseline assessment in the considered interval.

All ECG data (parameters and findings) are listed by treatment group, subject and visit. All post-treatment notable abnormalities are flagged and qualitative abnormalities (as transferred by the ECG central reader) are listed.

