#### **11.2.12 12-lead ECG, findings data**

The dataset contains the observations extracted from the EG Domain with Category equals to 'FINDING' and Method equals to '12 LEAD STANDARD', in an occurrence data structure. Each finding is mapped now into an event.

Findings are considered '**Treatment Emergent**' if the date/time of the ECG is after the first study treatment intake.

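### The SAP labels every 12-lead ECG finding after first dose as treatment-emergent by date alone, contrary to Protocol Appendix 7 and without declaring it; the Day 1 Holter rule has a similar weakness

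*SAP*

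**What the plan says.** **12-lead ECG, SAP.** Section 5.8.7.1, in the text after Table 7, says of the central cardiologist's findings: "All findings reported post first dose are considered as treatment-emergent". The derivation in SAP 11.2.12 matches. A finding is flagged "if the date/time of the ECG is after the first study treatment intake", with no other condition. SAP 10.9.3.1 then tabulates the flagged findings by treatment group: "The number and percentage of subjects with any treatment-emergent ECG qualitative abnormalities at any time", broken down by category and reported term.

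**12-lead ECG, protocol.** Appendix 7 lists the ECG abnormalities of interest and begins with "Morphological ECG findings (defined as any abnormal finding not present prior to start of treatment". Protocol 11.4.3.2.1 plans the matching output: "In addition treatment-emergent morphological ECG abnormalities will be summarized descriptively (using data from the ECG provider".

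**Holter.** SAP 5.8.7.2 says: "Each finding reported for the Holter-ECG performed on Day 1 are considered treatment-emergent". SAP 10.9.3.2 tabulates these by treatment group. The protocol plans the table in 11.4.3.2.3 ("Treatment-emergent abnormalities as assessed by 24-hour Holter ECG monitoring will be summarized by dose group and presented similarly to AEs") but does not say what makes a Holter finding emergent.

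**General rule.** Protocol 11.4.3 admits to the safety tables, by default, "only treatment-emergent safety data (observations with onset or assessment dates at/after first intake of study drug up to 6 weeks after study drug discontinuation".

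**The concern.** An abnormality seen before the first capsule and again afterwards did not emerge on treatment. Under a date-only rule it is still counted as though it had. The comparator data exist: every subject has a Screening and a Day 1 pre-dose 12-lead ECG and a 24-hour Holter at Screening, all centrally read.

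Entry criteria do not remove the problem. Exclusion criterion 4 covers rhythm disorders, with second- and third-degree AV block among its examples. It does not name first-degree block, bundle-branch block or ST-T changes, and SAP 5.8.7.1 says the central findings cover rhythm, ectopy, conduction and morphology.

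Emergent ECG and Holter abnormalities are named safety endpoints (Protocol 6.2), safety is a main objective, and first-dose effects on heart rate and AV conduction are recognised effects of the drug (Protocol 5.1.4.2). Background findings in every arm dilute a real contrast. With 12 subjects per dose, a chance imbalance in them can also look like a drug effect. The SAP plans no table of pre-dose qualitative findings from which a reader could subtract the background.

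**Working it through.** **1. Text comparison.** The plan states no figure on this point, so there is none to reproduce. The check sets the passages side by side.

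| Item | Protocol | SAP | Result |
|---|---|---|---|
| 12-lead qualitative finding | Appendix 7: must be absent before treatment | 5.8.7.1 and 11.2.12: dated after first intake | Contradiction |
| Holter finding | 6.2, 11.3.3 and 11.4.3.2.3 name the endpoint; no definition | 5.8.7.2: any finding on the Day 1 recording | Gap, not a contradiction |
| Declared as a change | n/a | Section 4: not listed | Undeclared |

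Section 4 does record other changes, including an added time-matched Holter heart-rate endpoint (4.3.4). The SAP thus uses the screening Holter as comparator for hourly heart rate but not for findings. The Day 1 recording also starts immediately before dosing (Protocol 7.2.3), so the Holter rule does not exclude a finding from its pre-dose minutes.

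**2. Chance that a persistent finding is picked up.** Scheduled post-dose 12-lead ECGs per subject: 6 hourly on Day 1, plus Weeks 2, 4, 8, 12 and EOS, so 6 + 5 = 11. A stable finding would almost certainly appear on at least one.

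**3. Illustration under assumed rates.** Let q be the assumed proportion of subjects with a persistent pre-dose finding of any kind. The documents give no value. Group sizes are from Protocol 11.6.1: 12 per dose and 16 on pooled placebo.

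- Expected miscounted subjects = 12q per dose and 16q on placebo.
- Chance of at least one in a dose group = 1 − (1 − q)^12.
- With assumed true new-onset rates of 20% on drug and 5% on placebo, independent of q, displayed rate = q + (1 − q) × new-onset rate.

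| q | Miscounted of 12 | Miscounted of 16 | P(at least 1 of 12) | Displayed, drug vs placebo | Risk ratio | Risk difference |
|---|---|---|---|---|---|---|
| 0 | 0 | 0 | 0 | 20% vs 5% | 4.0 | 15.0 points |
| 5% | 0.6 | 0.8 | 46% | 24.0% vs 9.8% | 2.46 | 14.2 |
| 10% | 1.2 | 1.6 | 72% | 28.0% vs 14.5% | 1.93 | 13.5 |
| 20% | 2.4 | 3.2 | 93% | 36.0% vs 24.0% | 1.50 | 12.0 |
| 30% | 3.6 | 4.8 | 99% | 44.0% vs 33.5% | 1.31 | 10.5 |

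The risk ratio shrinks sharply and the risk difference modestly.

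**4. Chance imbalance.** Suppose no drug effect and no new findings, with x of 12 in each dose group and y of 16 on placebo binomial with probability q. The chance that at least one of the four doses shows x/12 − y/16 of 20 points or more is the sum over y of P(y) × [1 − (1 − P(x/12 − y/16 ≥ 0.20))^4]. This is about 13%, 30% and 34% for q = 10%, 20% and 30%.

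Steps 3 and 4 pool all findings. The table also reports by category and term, and within one row q is the prevalence of that single term, which would be lower.

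**The case against.** **The protocol's general rule supports the SAP.** Protocol 11.4.3 accepts an assessment date after first intake, and the SAP rule meets it. But that sentence yields to anything more specific, and it sets the window of data entering the tables. Appendix 7 is the more specific text. The two are compatible: a finding can be required to be both in the window and new. Protocol 10.1.1 points the same way, because an ECG finding qualifies as an adverse event only if it is new or worse since study start.

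**Appendix 7 leaves definitions to the SAP.** It does so for the abnormal values to be reported, which reads most naturally as numeric thresholds. The morphological definition is already given there.

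**The key cardiac risks are analysed against baseline elsewhere.** This stands. Table 7 includes increases from baseline in PR and QTc, hourly Day 1 changes are summarised, and Holter heart rate is time-matched to Screening. First-degree AV block therefore has a baseline-referenced PR counterpart. Subject listings hold all findings, so a reader could identify pre-existing ones by hand.

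**Few serious pre-existing findings will get through.** This partly stands. Criterion 4 gives examples, not a closed list, and it covers many of the serious Holter terms in Table 13. The starred Table 13 items (quality codes, comments, other) are only listed.

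**The repair has its own cost.** This also stands. Requiring absence of the same term hides worsening under that term, and one 24-hour screening recording cannot prove that an intermittent finding is new. The present rule over-counts but does not miss new findings.

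A reader might infer that the SAP breaks a protocol definition for Holter as well. It does not: Appendix 7 speaks of morphological ECG findings, and no protocol text defines an emergent Holter finding.

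**Conclusion.** The point holds for 12-lead qualitative findings. The SAP's date-only rule contradicts Appendix 7, is not declared in Section 4, and causes persistent pre-dose abnormalities to be tabulated as emergent in every arm. For Holter, ignoring the screening recording is a weakness in the definition only.

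The reach is limited to descriptive tables of qualitative findings. The baseline-referenced PR, QTc and heart-rate analyses, the main pharmacodynamic test and the stopping rules do not use this flag.

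The size cannot be stated. The direction, inflation in every arm, follows from the rule itself. The figures above rest on assumed prevalences of 5% to 30% and assumed new-onset rates, and they pool terms that the table also reports separately. It is tempting to read them as showing that the cardiac safety conclusions will be distorted; the documents do not support that, because they give no prevalence and the main conduction and rate measures are referenced to baseline. This should be fixed because it decides which subjects count towards a named safety endpoint and the remedy is cheap, but it does not undermine the trial.

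**What to change.** **12-lead ECG (SAP 5.8.7.1 and 11.2.12).** Count a finding as treatment-emergent only if the same category and term is absent from all of the subject's pre-dose 12-lead ECGs, meaning Screening and Day 1 pre-dose. Keep every post-dose finding in the listings, with a flag for those already present before dosing.

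**Holter (SAP 5.8.7.2 and 11.2.14).** Either count a Day 1 finding as emergent only if it is absent from the screening Holter, or tabulate Day 1 findings beside Screening findings by treatment group. The second option avoids claiming that an intermittent finding is new on the strength of one earlier 24-hour recording.

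**If the date rule is kept.** Declare it in SAP Section 4 as a departure from Appendix 7, and add a table of pre-dose findings so that the background is visible.

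**Cost.** SAP wording and one merge of data already collected and centrally read. The drawback is that worsening of a pre-existing finding under an unchanged term would appear only in the listing.

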**5.8.7.2 24 hour Holter-ECG**

Holter-ECG monitoring is performed for 24 hours at Visit 1 (Screening) and at Visit 2 (Randomization/ Day 1). The 24 hour Holter-ECG parameter collected is the hourly mean heart rate (bpm).

The hourly records are time-matched between these two visits and the corresponding change for each matched time point is computed.

The following endpoints are defined:

- Occurrence of treatment-emergent Holter-ECG-Holter abnormalities on Day 1;
- Absolute time-matched hourly mean heart rate (bpm) change from Visit 1 (Screening) to Visit 2 (Randomization/ Day 1) at each hourly timepoint up to 24 hours post-dose for;

- Holter-ECG- variables

The following analysis parameter is defined:

- ECG Mean Heart rate (beats/min) .

For this analysis parameter, the following analysis variables are defined (see Section 11 for further details):

- Baseline value at each hourly time point (i.e. hourly measurements at Visit 1)
- Analysis value at each post-baseline assessment (i.e., hourly measurements at Visit 2)
- Absolute time-matched change from Visit 1 (Screening) to Visit 2 (Randomization/ Day 1) at each hourly time point.

- Holter-ECG qualitative findings

For each Holter-ECG, the cardiologist provides his overall interpretation (Normal/ Abnormal) and describes the potential findings in the comment section. Each finding reported for the Holter-ECG performed on Day 1 are considered treatment-emergent.

**5.8.8 Echocardiography**

Echocardiography is performed at Visit 1 (Screening) and Visit 6 (EOT). The presence/absence (i.e., Yes/No) of any abnormality is recorded in the eCRF.

### 5.8.9 Discharge from hospital at day 1/re-initiation

The subject's eligibility for discharge or study drug discontinuation at Visit 2 (Randomization/ Day 1) or study treatment re-initiation is independently assessed by the cardiac safety assessor and collected in the 'Discharge from Hospital at Day 1/Re-Initiation'. The variables of interest are:

- Actual time from first study treatment intake to discharge (hours);
- Time from first study treatment intake to discharge, derived from the actual time computed above (at 6 hours, after 6 through 12 hours, after 12 hours);
- Reason for non-discharge at 6 hours, as collected in the eCRF;
- Reason for non-discharge from 6 to 12 hours, as collected in the eCRF;

### 5.8.10 Laboratory

Laboratory test results are transferred from the central laboratory or, if assayed locally, entered in local laboratory eCRF. Assessments are performed at each scheduled visit from Visit 1 (Screening) to Visit 7 (EOS), and at unscheduled visits if required.

The following parameters are assayed:

- **Hematology:** Hemoglobin, hematocrit, platelets, MCH, MCV, MCHC, reticulocytes/erythrocytes, erythrocytes, leukocytes count with differential count (basophils, eosinophils, lymphocytes, neutrophils, monocytes, and basophils/ leukocytes, eosinophils/ leukocytes, lymphocytes/ leukocytes, monocytes/ leukocytes, neutrophils/ leukocytes);
- **Blood chemistry:** Aspartate aminotransferase (AST), alanine aminotransferase (ALT), alkaline phosphatase, total bilirubin (TBL), direct bilirubin, lactate dehydrogenase, creatinine, blood urea nitrogen, urate, glucose, cholesterol, triglycerides, sodium, potassium, chloride, calcium, protein, albumin, creatinine clearance;
- **Coagulation tests:** prothrombin time, INR, activated partial thromboplastin time;
- **Urine protein-to-creatinine ratio** (Visits 1, 2 and 6): Creatinine, protein, protein/ creatinine.

For women of childbearing potential, serum pregnancy tests are performed at Visit 1 (Screening) and Visit 7 (EOS) (central laboratory), and urinary pregnancy tests are performed at all other visits and collected in the dedicated eCRF page.

Urine dipsticks are used to perform the urinalysis at all visits (e.g., pH, glucose, proteins, blood, leukocytes) and the results are recorded in the dedicated eCRF page.

The following endpoints are defined:

- Absolute value and absolute change from baseline in laboratory parameters (hematology, blood chemistry, and urinalysis) at each post-baseline analysis visit up to EOS;
- Treatment-emergent laboratory test abnormalities based on reference ranges (central laboratory) and abnormality thresholds (as defined in appendix 7 of the study protocol and in Section 15.2).

For these abnormalities, additional criteria are defined to characterize the occurrence of treatment-emergent abnormalities during the treatment period in each direction separately (low and high).

Treatment-emergent liver function abnormalities occurring at any time post-baseline are identified according to the following criteria, where a subject is considered to have met the criteria if they have at least one abnormality based on the worst post-baseline value measured (up to EOS):

- ALT  $\geq 3, \geq 5, \geq 8 \times$  ULN;
- AST  $\geq 3, \geq 5, \geq 8 \times$  ULN;
- AST or ALT  $\geq 3, \geq 5, \geq 8, \times$  ULN;
- ALP  $\geq 2 \times$  ULN;
- TBL  $\geq 2 \times$  ULN;
- TBL  $\geq 2$  ULN combined with ALT  $\geq 3$  ULN;
- TBL  $\geq 2$  ULN combined with AST  $\geq 3$  ULN;
- INR  $\geq 1.5, \geq 2.5 \times$  ULN;
- INR  $\geq 1.5, \geq 2.5 \times$  baseline;
- INR  $\geq 1.5$  ULN combined with ALT  $\geq 3$  ULN;
- INR  $\geq 1.5$  ULN combined with AST  $\geq 3$  ULN;
- ALT  $\geq 3 \times$  ULN + TBL  $\geq 2 \times$  ULN + ALP  $< 2 \times$  ULN;
- AST  $\geq 3 \times$  ULN + TBL  $\geq 2 \times$  ULN + ALP  $< 2 \times$  ULN;

Please note that for criteria combining several parameters, the abnormality must be reported at the same visit (same sample date).

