**Table 5**      **Thresholds for marked laboratory abnormalities for ACT-334441**

Parameter	LL	LLL	HH	HHH
Hemoglobin	< 100 g/L (< 10g/dL; < 6.2 mmol/L)	< 80 g/L (<8g/dL; < 4.9 mmol/L)	Increase in > 20 g/L above ULN or above baseline (if baseline is above ULN)	Increase in > 40 g/L above ULN or above baseline (if baseline is above ULN)
MCH	ND	ND	ND	ND
MCV	ND	ND	ND	ND
MCHC	ND	ND	ND	ND
Hematocrit	< 28% (female) < 32% (male)	< 20%	> 60% (male) > 55% (female)	> 65%
Platelet count	< 75 × 10 e9 /L (< 75,000/mm  )	< 50.0 × 10 e9 /L (<50,000/mm  )	> 600 × 10 e9 /L	> 999 × 10 e9 /L
RBC count	ND	ND	ND	ND
WBC count	ND	< 1.9 × 10 e9 /L	> 20.0 × 10 e9 /L (>20 000/mm  )	CTCAE (grade 3) > 100.0 × 10 e9 /L (>100 000/mm  )
Lymphocyte	ND	< 0.2 × 10 e9 /L (< 200/mm  ) ALERT* < 0.2 × 10 e9 /L (< 200/mm  )	> 4.0 × 10 e9 /L (> 4000/mm  )	≥ 8 × 10 e9 /L (> 8000/mm  )
Neutrophils	< 1.5 × 10 e9 /L (< 1,500/mm  )	< 1.0 × 10 e9 /L (< 1000/mm  )	ND	ND
Eosinophils	ND	ND	> 5.0 × 10 e9 /L or > 5% (> 5000 cells/mm  )	ND
Monocytes	ND	ND	ND	ND
Basophils	ND	ND	ND	ND
Polymorphonuclear leucocyte/Band cells	ND	ND	> 90%	> 95%
AST	ND	ND	≥ 3 ULN (U/L) ALERT ≥ 3 ULN	≥ 5 ULN (U/L) ALERT ≥ 5 ULN ≥ 8 ULN
ALT	ND	ND	≥ 3 ULN (U/L) ALERT ≥ 3 ULN	≥ 5 ULN (U/L) ALERT ≥ 5 ULN ≥ 8 ULN
Total bilirubin	ND	ND	≥ 2 ULN (umol/L) ALERT ≥ 2 ULN combined with ALT or AST ≥ 3 ULN	≥ 5 ULN (umol/L)
Alkaline Phosphatase	ND	ND	> 2.5 ULN (U/L)	> 5 ULN (U/L)

Confidential

INR	ND	ND	≥ 1.5 ULN** or ≥ 1.5 times above baseline if on anticoagulation ALERT ≥ 1.5 combined with ALT or AST ≥ 3 ULN	≥ 2.5 ULN** or ≥ 2.5 times above baseline if on anticoagulation
Activated partial thromboplastin time prolonged (aPTT)	ND	ND	> 1.5 - 2.5 × ULN	> 2.5 × ULN
Lactate dehydrogenase	ND	ND	ND	ND
Creatinine	ND	ND	> 1.5 ULN (umol/L) or > 1.5 × baseline	> 3 ULN (umol/L) or > 3 × baseline
Creatinine Clearance (eGFR)	<60 ml/min/1.73m 	<30 ml/min/1.73m 	ND	ND
Urea	ND	ND	> 2.5 ULN (mmol/L)	> 5 ULN (mmol/L)
Uric acid	ND	ND	> 0.59 mmol/L (>10 mg/dL)	> 0.72 mmol/L (>12 mg/dL)
Proteinuria	ND	ND	≥1.0 g/24h	≥3.5 g/24h
Protein/creatinine ratio	ND	ND	>100 mg/mmol***	>300 mg/mmol***

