Albumin	< 30 (g/L)	< 20 (g/L)	ND	ND
Protein total	ND	ND	ND	ND
C-reactive protein	ND	ND	ND	ND
Glucose (Non-diabetic Fasting)	< 3.0 (mmol/L) (< 55 mg/dL)	< 2.2 (mmol/L) (< 40 mg/dL)	> 8.9 (mmol/L) (> 160 mg/dL)	> 13.9 (mmol/L) (> 250 mg/dL)
Potassium	< 3.2 (mmol/L)	< 3.0 (mmol/L)	> 5.5 (mmol/L)	> 6.0 (mmol/L)
Sodium	ND	< 130 (mmol/L) (< 130 mEq/L)	> 150 (mmol/L) (> 150 mEq/L)	> 155 (mmol/L) (> 155 mEq/L)
Calcium (corrected for albumin)	< 2.0 (mmol/L) (< 8.0 mg/dL)	< 1.75 (mmol/L) (< 7.0 mg/dL)	> 2.9 (mmol/L) (> 11.5 mg/dL)	> 3.1 (mmol/L) (> 15.5 mg/dL)
Chloride	ND	ND	ND	ND
Triglyceride	ND	ND	> 3.42 (mmol/L)	> 11.4 (mmol/L)
Cholesterol	ND	ND	> 7.75 (mmol/L)	> 12.92 (mmol/L)
Fibrinogen	< 0.75 - 0.5 LLN or 25 - < 50% decrease from baseline	< 0.25 LLN or < 75% decrease from baseline or absolute value < 50 mg/dL	ND	ND
IgG	ND	ND	ND	ND
IgM	ND	ND	ND	ND
IgA	ND	ND	ND	ND

ANA	ND	ND	ND	ND
Anti-dsDNA	ND	ND	ND	ND
C3	ND	ND	ND	ND
C4	ND	ND	ND	ND
Anti-Sm	ND	ND	ND	ND
Antiribosomal P	ND	ND	ND	ND
Anti-cardiolipin IgA	ND	ND	ND	ND
Anti-cardiolipin IgG	ND	ND	ND	ND
Anti-cardiolipin IgM	ND	ND	ND	ND
Serum pregnancy test	ND	ND	ND	Positive ALERT: Positive

ALT = alanine aminotransferase; ANA = anti-nuclear antibodies; anti-dsDNA = anti-double-stranded DNA; anti-Sm = anti-Smith; aPTT = activated partial thromboplastin time; AST = aspartate aminotransferase; CTCAE = Common Terminology Criteria for Adverse Events; eGFR = estimated glomerular filtration rate; INR = international normalized ratio; MCH = mean corpuscular hemoglobin; MCHC = Mean corpuscular hemoglobin concentration; MCV = mean corpuscular volume; ND = not defined; RBC = red blood cell; ULN = upper limit of normal; WBC = white blood cell.

\*If lymphocyte count < 800 cells/ $\mu$ l at EOS visit, an alert will be sent.\*\* HH and HHH based on CTCAE 2010 v4.03 [CTCAE 2010]. However, an Alert will be sent when INR  $\geq$  1.5 based on the guidance for monitoring liver test abnormalities from Food and Drug Administration (FDA) [FDA 2009]. \*\*\*Source for protein/creatinine ratio thresholds: <http://www.renal.org/information-resources/the-uk-eckd-guide/proteinuria#sthash.jdT5cPIP.dpbs>.

[figure not shown]

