| CHEMISTRY   | URATE     | Urate                                 | umol/L                     | M   | NA     | NA    | 262  | 452  | > 590                                | > 720                            |
| COAGULATION | APTT      | Activated Partial Thromboplastin Time | sec                        |     | NA     | 14.0  | 24   | 37   | > 1.5 - 2.5 $\times$ ULN             | > 2.5 $\times$ ULN               |

| Category    | Test Code | Test Name                          | Standard Unit | Se x | LLL  | LL  | LO     | HI     | HH   | HHH  |
|-------------|-----------|------------------------------------|---------------|------|--|---|--------|--------|--|--|
| COAGULATION | FIBRINO   | Fibrinogen                         | g/L           |      | < 0.25 LLN or < 75% decrease from baseline or absolute value < 0.5 | < 0.75 - 0.5 LLN or 25 - < 50% decrease from baseline | 2.1    | 4.7    | 6.0  | NA   |
| COAGULATION | INR       | Prothrombin Intl. Normalized Ratio | Fraction of 1 |      | NA   | NA  | 0.8    | 1 2    | $\geq 1.5$ ULN   | $\geq 2.5$ ULN   |
| COAGULATION | PT        | Prothrombin Time                   | sec           |      | NA   | NA  | 9.4    | 13     | NA   | 100.1  |
| HEMATOLOGY  | EOS       | Eosinophils                        | 10e9/L        |      | NA   | NA  | 0      | 0 5    | > 5.0  | ND   |
| HEMATOLOGY  | HCT       | Hematocrit                         | L/L           | F    | < 20   | < 28  | 0.36 4 | 0.48 9 | > 55   | > 65   |
| HEMATOLOGY  | HCT       | Hematocrit                         | L/L           | M    | < 20   | < 32  | 0.41 6 | 0 54 1 | > 60   | > 65   |
| HEMATOLOGY  | HGB       | Hemoglobin                         | g/L           | F    | < 80 g/L   | < 100 g/L   | 115    | 160    | Increases in > 20 g/L above ULN or Increases in > 20 g/L above baseline (if baseline is above ULN) | Increases in > 40 g/L above ULN or Increases in >40g/L above baseline (if baseline is above ULN) |

| Category   | Test Code | Test Name          | Standard Unit | Sex | LLL    | LL    | LO   | HI   | HH   | HHH   |
|------------|-----------|--------------------|---------------|-----|--------|-------|------|------|--|---|
| HEMATOLOGY | HGB       | Hemoglobin         | g/L           | M   | < 80   | < 100 | 130  | 175  | Increases in > 20 g/L above ULN or Increases in > 20 g/L above baseline (if baseline is above ULN) | Increases in > 40 g/L above ULN or Increases in > above baseline (if baseline is above ULN) |

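### The SAP's combined liver rows use INR ≥ 1.5 × ULN while the protocol's liver alert uses absolute INR ≥ 1.5, so some alerted samples are not identified in those rows

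*SAP*

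**What the plan says.** **Protocol, Appendix 7, Table 5.** The INR row carries two kinds of limit. The marked-abnormality grades are multiples of ULN: HH at 1.5 and HHH at 2.5, with a baseline-relative version for subjects on anticoagulation. The liver alert is set separately, as "≥ 1.5 combined with ALT or AST ≥ 3 ULN". The footnote attributes the grades to CTCAE and then sets the alert apart from them: "However, an Alert will be sent when INR $\geq$ 1.5 based on the guidance for monitoring liver test abnormalities". The absence of a ULN multiple in the alert therefore looks deliberate.

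**SAP, section 5.8.10.** The list of liver function abnormalities includes "INR $\geq 1.5$ ULN combined with ALT $\geq 3$ ULN" and the same row with AST. It also has single-parameter rows: ALT, AST, and either of them at 3, 5 and 8 × ULN; INR at 1.5 and 2.5 × ULN; and INR at 1.5 and 2.5 × baseline. No row combines absolute INR ≥ 1.5 with ALT or AST ≥ 3 × ULN.

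**SAP, section 15.2.1, Table 16.** The row for "Prothrombin Intl. Normalized Ratio" gives a reference range from 0.8 to a value extracted as '1 2', with HH at 1.5 × ULN.

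**SAP, section 4.** The changes and clarifications listed there do not mention the INR limit.

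**The concern.** The SAP takes the × ULN multiple that the protocol uses for grading and places it in the combined criterion, where the protocol's alert uses an absolute value. With any INR upper limit above 1.0 the SAP criterion is the stricter of the two. The trial could then send alerts for raised transaminases with INR ≥ 1.5 while the report shows no subject in either combined INR row. A reader comparing the alerts with the tables would have no explanation for the difference. The stake is whether the report can identify the joint cases that the trial itself flagged.

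**Working it through.** The documents state no derived INR figure to reproduce, so the check is threshold arithmetic.

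**Inputs**
- SAP combined criterion: INR ≥ 1.5 × ULN with ALT (or AST) ≥ 3 × ULN (SAP 5.8.10).
- Protocol alert: absolute INR ≥ 1.5 with ALT or AST ≥ 3 × ULN (Protocol Table 5 and footnote).
- INR upper limit: 1.2, read from '1 2' in SAP Table 16. This is an assumption about a lost decimal point. The eosinophil upper limit in the same table, '0 5', is damaged in the same way.

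**Step 1: SAP cut-off.** 1.5 × ULN = 1.5 × 1.2 = 1.8.

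**Step 2: gap.** The alert starts at 1.5 and the SAP row at 1.8. With ALT or AST ≥ 3 × ULN on the same sample, INR from 1.5 to just under 1.8 meets the alert and misses both combined rows.

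**Step 3: sensitivity to the upper limit.**

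| INR ULN | 1.5 × ULN | Band alerted but not in the combined rows |
|---|---|---|
| 1.0 | 1.50 | none |
| 1.1 | 1.65 | 1.50 to < 1.65 |
| 1.2 | 1.80 | 1.50 to < 1.80 |
| 1.3 | 1.95 | 1.50 to < 1.95 |

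The two limits coincide only at a ULN of 1.0, so the mismatch does not depend on reading the damaged cell as exactly 1.2.

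**Step 4: where these samples still appear.** The alert requires ALT or AST ≥ 3 × ULN, so every such sample is counted in an ALT or AST row. The INR ≥ 1.5 × baseline row catches part of the band, depending on the subject's baseline:

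| Baseline INR | 1.5 × baseline | Part of the 1.5 to < 1.8 band caught |
|---|---|---|
| ≤ 1.0 | ≤ 1.50 | all |
| 1.1 | 1.65 | upper half (1.65 and above) |
| 1.2 | 1.80 | none |

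That row looks at INR alone, so it does not show that transaminases were raised on the same sample.

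**Step 5: scale within the combined rows.** With 12 subjects planned per active dose, one case is 1/12 = 8.3% of a group, against 0% if it is not identified. This shows what one case does to those rows; it does not estimate how many cases will occur.

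**The case against.** The strongest defence is that Appendix 7 gives grades and alerts different purposes. The marked-abnormality grades serve flagging and standardized analysis and reporting, while an alert is a threshold at which the investigator must act. The SAP's 1.5 × ULN is the protocol's HH grade, and using a reporting grade in a report is defensible. That much stands: the SAP's limit is not shown to be wrong. It does not explain why no row matches the alert combination, or why SAP section 4 is silent about it.

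Four stronger readings are tempting, and the documents do not support them.

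- *Alerted cases go uncounted.* They are counted in the ALT or AST rows, and SAP 10.9.4 puts all laboratory data in listings. Only the joint label is missing.
- *A promised FDA-based endpoint is altered.* The protocol endpoint names the FDA guidance for ALT, AST and bilirubin only (Protocol 6.2 and 11.4.3.5.2). For bilirubin with transaminases the SAP matches Table 5.
- *The liver stopping criterion is weakened.* Protocol Table 4 points to Protocol 5.1.10.5, which works through central-laboratory alerts. The SAP criteria do not drive it.
- *The SAP contradicts itself on timing.* It judges subjects "if they have at least one abnormality based on the worst post-baseline value measured (up to EOS" and then adds "Please note that for criteria combining several parameters, the abnormality must be reported at the same visit (same sample date". The second is a specific rule that qualifies the first for combinations, so a programmer has nothing to resolve. The documents give no time window for pairing results from different dates, and asking for one would be a preference.

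SAP 10.9.4 also refers to Protocol Figure 3 for liver thresholds. The figure is not available here, so its INR wording could not be checked.

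**Conclusion.** The mismatch is real and limited. The SAP's two combined INR rows start at 1.5 × ULN, which is 1.8 if the ULN is 1.2; the protocol's alert starts at 1.5. Samples with INR from 1.5 to just under 1.8 and ALT or AST ≥ 3 × ULN are alerted but not identified as combined cases. The width of the band rests on reading the damaged Table 16 cell as 1.2; its existence needs only a ULN above 1.0. The comparison uses Table 5 and its footnote and takes both results from one sample. The consequence is confined to the labelling of joint cases in the report.

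**What to change.** In SAP 5.8.10, add two rows: absolute INR ≥ 1.5 combined with ALT ≥ 3 × ULN, and the same with AST, on the same sample date as the existing combinations. These match the Table 5 alert. Keep the × ULN rows for grading.

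The cost is two extra table rows and a small programming change on data already collected. With a ULN of 1.0 or more, every sample that meets the × ULN rows also meets the new ones, so the combined count can only stay the same or rise. No alert, stopping rule or patient management changes.
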